The first set of regressions will be used to identify baseline characteristics associated with missing primary outcome data at any post treatment time point. The second will be used to identify baseline characteristics associated with missing primary outcome data at the primary endpoint (12 months) only. The third set will be used to identify baseline characteristics associated with withdrawal prior to treatment. Any baseline variables that are found to improve model fit (compared with the model with all parameters other than the intercept constrained to zero (not omitted)) in a likelihood ratio test of size 10%, will be added as fixed effects to the primary analysis model, and this model refitted. The results of this analysis will be reported in a similar manner to the reporting of the primary analysis (Appendix E-2).

We will also refit the primary analysis model using a multiply imputed dataset. A total of 250 imputations will be generated using multiple imputation by chained equations. The longitudinal structure of the data

will be accounted for by imputing the data in “wide” format. Further clustering by centre will be ignored for the purposes of the imputation model, (given that between centre heterogeneity is expected to be small and is not the focus of the analysis) but will be allowed for in the substantive analysis models fitted to each of the imputed datasets. Imputation will be carried out separately by randomised group to allow for possible interactions between randomised group and other variables included in the imputation model. Only patients that did not withdraw prior to treatment delivery will have their outcome data imputed, although patients that withdrew prior to treatment will be included in the imputation model. Patients who die during follow up will not have outcome data imputed following death. The variables that will be included in the imputation model are given in Table 3. Any baseline variables that are identified as being associated with missingness of post treatment PEM scores and/or non-receipt of treatment (see above) will also be included. Missing values in baseline variables included in the imputation model will be imputed as necessary (with any values imputed via single imputation methods for other analyses removed).

**Table 3:** Details of variables included in the imputation model

Variable	Type	Details	Univariate model (if imputation required)

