Post-treatment PEM scores (four time points)	Continuous	Percentage disability (0 – 100)	Predictive mean matching (10 nearest neighbours)
Reference joint	Binary	MCP = 0, PIP = 1	N/A (complete)
Baseline PEM score	Continuous	Percentage disability (0 – 100)	Predictive mean matching (10 nearest neighbours)
Treatment delivery PEM score	Continuous	Percentage disability (0 – 100)	Predictive mean matching (10 nearest neighbours)
Baseline URAM score	Continuous	Integer score between 0 and 45	Predictive mean matching (10 nearest neighbours)
Post-treatment URAM scores (four time points)	Continuous	Integer score between 0 and 45	Predictive mean matching (10 nearest neighbours)
Baseline MHQ score	Continuous	Overall MHQ score between 0 and 100	Predictive mean matching (10 nearest neighbours)
Post-treatment MHQ score (two time points)	Continuous	Overall MHQ score between 0 and 100	Predictive mean matching (10 nearest neighbours)
Passive extension of reference joint at baseline	Continuous	Mean of the available passive extension measurements taken of the reference joint at baseline	Linear regression
Passive extension of reference joint at treatment delivery and 3, 6, 12 and 24 months post-treatment	Continuous	Mean of the available passive extension measurements taken of the reference joint at treatment delivery and 3, 6, 12 and 24 months post-treatment	Linear regression
Active extension of reference joint at baseline	Continuous	Mean of the available active extension measurements taken of the reference joint at baseline	Linear regression
Active extension of reference joint at treatment delivery and 3, 6, 12 and 24 months post-treatment	Continuous	Mean of the available active extension measurements taken of the reference joint at treatment delivery and 3, 6, 12 and 24 months post-treatment	Linear regression
Flexion of reference joint at baseline	Continuous	Mean of the available flexion measurements taken of the reference joint at baseline	Linear regression
Flexion of reference joint at treatment delivery and 3, 6, 12 and 24 months post-treatment	Continuous	Mean of the available flexion measurements taken of the reference joint at treatment delivery and 3, 6, 12 and 24 months post-treatment	Linear regression

Crossover	Binary	Did not receive allocated treatment = 0, Received allocated treatment = 1	Logistic regression (with data augmentation if necessary)
Complications	Binary	No complication = 0, Complication = 1	Logistic regression (with data augmentation if necessary)

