#### **8.4.7 Recurrence**

Recurrence will be defined in a binary manner (recurred or not recurred) at 6, 12 and 24 months post-treatment. Recurrence at the 6 month follow up is defined as an increase in passive extension deficit of the reference joint of 6° since the 3 month post treatment follow up. Recurrence at 12 and 24 months is defined as an increase in passive extension deficit of the reference joint of 20° since the 3 month post treatment follow up. These binary outcomes will be modelled using mixed effect logistic regression models adjusting for study reference joint (MCP or PIP), study reference digit, baseline PEM score and baseline passive extension measurement as fixed effects with centre as a random effect. These models will include all participants for whom the relevant (i.e. month 6 or month 12) binary indicator of recurrence can be derived using the available data. If perfect prediction occurs due to empty strata at some covariate combinations, then participants with study reference digit indicated as middle, index or thumb will be pooled so that reference digit becomes a three category covariate (little, ring, other). If the issue persists, then the term for study reference digit will be dropped from the model. If the baseline PEM score and/or baseline passive extension measurement is missing, then they will be imputed using predicted values via regression of the observed values on observed baseline MHQ scores and reference joint (MCP or PIP). If the MHQ score is also missing, then missing baseline PEM scores and/or baseline passive extension measurements will be imputed using predicted values via regression of the observed values on the observed baseline URAM scores and reference joint. If baseline URAM score is also missing then missing baseline PEM scores and/or baseline passive extension measurements will be imputed with the reference joint strata specific means. For both analyses, the estimated odds ratios for allocation (and two-sided 95% CIs) will be reported. This model will also be used to derive the absolute differences in risk of recurrence (together with two-sided 95% CIs) at representative values of the covariates (mean of the continuous covariates, both levels of reference joint, two levels of reference digit (ring or little) and marginalising over the centre random effects). We will also test composite null hypotheses about the absolute difference in incidence of recurrence at 12

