and 24 months post-treatment. Specifically we will report one-sided p-values from four Wald tests of  $H_0: d \geq 10\%$  , where  $p < 0.025$  indicates statistical significance, and  $d = \Pr(\text{Recurrence} \mid \text{Collagenase}, X) - \Pr(\text{Recurrence} \mid \text{Surgery}, X)$  for the four covariate patterns  $X$  outlined above (MCP + Ring, MCP + Little, PIP + Ring, PIP + Little).

Due to the Coronavirus pandemic, a substantial proportion of participants were followed up remotely at 3, 6, 12 and 24 months post-treatment, and did not have goniometric measurements taken. Missingness due to remote follow up, as well as attrition, mean a substantial proportion of the post-treatment goniometric measurement data will be missing. The proportion of missing data at each time point will be summarised by randomised group, as will the available reasons this missing data. The principal analyses of recurrence outlined above (based on the available goniometric measurements) will be repeated using two alternative analysis sets. The first analysis set will supplement the available goniometric measurements with measurements obtained using photographs taken by clinical investigators. If photographs taken by the clinical investigators are not available, then measurements obtained using photographs taken by the participant will be used (note this would include photographs submitted by participants in the photography sub-study, as well as photographs submitted by non-sub-study participants who could not attend clinic visits due to the pandemic). The second analysis will use the multiply imputed dataset(s) generated as part of the analyses specified in Section 8.3.1. Both analysis sets will be analysed using the same models used for the analysis of the available goniometric measurements, with estimates and tests being reported analogously.

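### In the multiply imputed recurrence analysis, recurrence for participants with missing goniometry rests on an unchecked normality assumption for passive extension

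*SAP*

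**What the plan says.** Section 8.3.1 specifies the imputation: "A total of 250 imputations will be generated using multiple imputation by chained equations". It also states that "Imputation will be carried out separately by randomised group". Table 3 gives a univariate model for each variable. The PEM, URAM and MHQ scores get "Predictive mean matching (10 nearest neighbours"). The row for "Passive extension of reference joint at treatment delivery and 3, 6, 12 and 24 months post-treatment" gets "Linear regression", as do the baseline row and the active extension and flexion rows. The section plans trace plots to judge burn-in. It plans no transformation, bound or distributional check for the angles, and Table 3 contains no recurrence indicator.

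Section 8.4.7 defines the outcome: "Recurrence at the 6 month follow up is defined as an increase in passive extension deficit of the reference joint" of 6° since month 3, and "Recurrence at 12 and 24 months is defined as an increase in passive extension deficit of the reference joint of 20" degrees since month 3. It expects a substantial share of goniometry to be missing and adds two alternative analysis sets. The first adds angles measured on photographs. For the second, "The second analysis will use the multiply imputed dataset(s) generated as part of the analyses specified in Section 8.3.1". The same logistic models are applied to both, with estimates and tests reported in the same way. The tests against the 10% margin are at 12 and 24 months only, so both are at the 20° cut. Section 8 links 12-month recurrence to a key secondary objective, and the recurrence table in Appendix F has multiply imputed rows for months 6 and 12.

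**The concern.** A regression coefficient or a mean tolerates a wrong residual shape fairly well. The probability of exceeding a threshold does not. In the analysis for which Table 3 was written, the angles are only auxiliary predictors of missing PEM scores, and linear regression is a reasonable choice there. Section 8.4.7 turns the same imputed angles into an outcome and cuts them, and the angle model is not revisited.

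Suppose most joints change little after month 3 and a few change a lot. A normal model with one residual variance then spreads the variance produced by the few over everyone. Many stable joints are drawn past 6°, and the number drawn past 20° may be too small or too large, depending on the shape. The imputed set is one of only two analyses meant to show whether missing goniometry matters, and it is read against a non-inferiority margin.

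**Working it through.** **No figure to reproduce.** The SAP states no recurrence rate, no distribution of angle change and no missing fraction. All shapes and the 30% and 50% missing fractions below are assumptions.

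**Closed-form check, mixture shape.** Assume a share p recurs by a mean of 30° (SD 10°), the rest have mean change 0°, and measurement error adds an SD of 4° to every difference. Recurrers then have variance 10² + 4² = 116 and the others 16. Assume also that the change is unrelated to the predictors, so that linear regression in effect draws from a normal with the overall mean and variance:

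- mean = 30p; variance = 16(1 − p) + 116p + 900p(1 − p)
- p = 10%: mean 3.0, variance 14.4 + 11.6 + 81 = 107, SD 10.34
- p = 5%: mean 1.5, variance 15.2 + 5.8 + 42.75 = 63.75, SD 7.98

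True rate at cut c = (1 − p)·[1 − Φ(c/4)] + p·[1 − Φ((c − 30)/√116)]. Normal-draw rate = 1 − Φ((c − mean)/SD). With half missing, the overall rate is the average of the two.

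| Cut | p | True | Normal draw | Overall, 50% missing | Simulated overall |
|---|---|---|---|---|---|
| 20° | 5% | 4.1% | 1.0% | 2.6% | 2.7% |
| 20° | 10% | 8.2% | 5.0% | 6.6% | 6.5 to 6.8% |
| 6° | 5% | 11.3% | 28.7% | 20.0% | 19.5% |
| 6° | 10% | 15.9% | 38.6% | 27.2% | 26.8 to 27.1% |

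The last column comes from two simulations of 320 per arm that imputed month 12 from month 3. In the first of them, the 20° difference between p = 10% and p = 5% hardly moved: 8.1 − 4.2 = 3.9 points true, 6.5 − 2.7 = 3.8 with linear regression. The 6° difference went from 4.5 to 7.3 points. The 6° rows use a 12-month change distribution, so for the 3-to-6-month outcome they only illustrate the mechanism.

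**Closed-form check, spike shape.** Assume 60% have exactly zero change and 40% an exponential change with mean θ, set so that 0.4·exp(−20/θ) is the true 20° rate. Mean = 0.4θ; variance = 0.8θ² − (0.4θ)².

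- True 10%: θ = 14.43, mean 5.77, SD 11.54, z = (20 − 5.77)/11.54 = 1.23, normal-draw rate 10.9%, overall 10.4% (simulated 10.3%).
- True 20%: θ = 28.85, mean 11.54, SD 23.08, z = 0.37, normal-draw rate 35.7%, overall 27.9% (simulated 27.6%).

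The true difference of 10 points becomes 27.9 − 10.4 = 17.5 (simulated 17.2).

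**Wider simulation.** 355 per arm (710/2), month 12 missing completely at random, imputed from month 3 and joint type. Overall 20° rates with 50% missing:

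- Normal change, linear regression: 5.1% true against 5.2%; 30.0% against 30.4%.
- Non-normal shapes, linear regression: 5% becomes 3.5 to 3.9%; 10% becomes 8.5 to 10.3%; 20% becomes 18.7 to 27.6%.
- 20° risk difference, true value about 10 points, 30% or 50% missing, linear regression: 9.6 to 10.5 (mixture), 11.3 to 13.2 (shifted exponential), 13.2 to 17.2 (spike).
- Predictive mean matching (PMM): 20° rates within about 1 point of the truth, 6° rates within about 2 points, risk differences 9.6 to 10.7.

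**Limit of PMM on the absolute angle.** In a further mixture check with 50% missing, the 6° rate was 11.0% true, 20.2% linear and 11.9% PMM with month-3 angle and joint type as predictors. With month-6 angle, PEM and baseline angle added, it was 11.3%, 19.3% and 16.2%, and the 20° rate was 8.2%, 7.2% and 7.1%. A likely reason is that donors are then matched on a predicted angle to which several variables contribute. A donor with a different month-3 angle lends an angle that no longer gives a realistic change for the recipient.

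**The case against.** A reader might infer that the imputed recurrence rates would reflect a normal tail and not the data. The SAP does not support that. Participants with both angles observed keep their real status, and the regression mean and residual variance are estimated from the data within each arm. Only the imputed share depends on normality.

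A reader might also infer that linear regression always gives too few 20° recurrences and so distorts the margin tests in a known direction. That does not stand either. The 20° error goes both ways across shapes, vanishes under normality, and leaves the risk difference almost unchanged in the mixture. The large 6° inflation falls on an outcome with no margin test.

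It is fair to add that every shape is assumed, that most of the simulations used few predictors where Table 3 has many, and that the spike shape at high rates implies very large changes among those who change, so it marks an extreme. The stakes are limited: this is the second alternative set for a secondary outcome.

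What remains is that the plan thresholds a normal draw, plans no check of it, and already uses a less shape-dependent method for the questionnaire scores in the same table.

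**Conclusion.** The point holds in a limited form. For participants with missing goniometry, recurrence in the multiply imputed analysis depends on an unchecked normality assumption. If changes since month 3 are close to normal given the predictors, the bias is negligible. If they are skewed or a mixture, and 30 to 50% of angles are missing, the 6° rate can be clearly inflated. The 20° rate and risk difference can then shift in either direction, from almost nothing to several points against the 10% margin. The actual size cannot be derived from the SAP. The principal recurrence analysis, which uses the available goniometry, and the primary PEM analysis are not affected. This is a cheap improvement of minor to moderate severity.

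**What to change.** In the passive extension rows of Table 3, replace linear regression by predictive mean matching with 10 nearest neighbours, as the table already specifies for the questionnaire scores. Preferably apply it to the change in passive extension since month 3, because the change is what is thresholded. In that case let the change replace the later angle in the imputation model, not stand beside it, and recover the later angle by addition. Add one sentence to section 8.3.1 requiring a comparison of observed and imputed distributions of change, by arm and visit.

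The cost is two table cells and one sentence, or slightly more programming if the change is imputed. PMM can slightly understate variance when donors are few, which the SAP already accepts for the questionnaire scores. On the absolute angle it reduces the error but does not always remove it. Active extension and flexion are analysed as continuous outcomes and need no change on this ground.

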## **2. Design**

DISC is a multi-centre, parallel group, individually randomised controlled non-inferiority trial of collagenase injection and manipulation versus limited fasciectomy surgery for the treatment of Dupuytren's contracture. In addition to the main study, DISC contains a qualitative sub study and a photography sub study. This plan outlines the pre-specified analyses of the main trial and the photography sub study. Eligible and consenting patients will be randomised 1:1 to either collagenase injection and manipulation or limited fasciectomy surgery, using a secure randomisation service. Due to the nature of the interventions under investigation, it is not possible to blind clinicians or participants to their treatment allocation. Both treatments should be delivered within 18 weeks of randomisation (as per referral to treatment time), however where possible sites should deliver treatment within 12 weeks of randomisation. Participants will be followed up at 2 and 6 weeks post treatment and 3, 6, 12 and 24 months post treatment. A flow diagram illustrating the flow of participants through the study is presented in Appendix A.

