## **3. Sample size**

The primary outcome for DISC is the score obtained for the 11 items in part two of the PEM at 12 months post treatment. Previous survey data collected from a representative sample of 880 patients with Dupuytren's Contracture showed the standard deviation of the scores for the 11 items in part 2 of

the PEM at baseline to be 22 points (unpublished). We estimate that a 6 point difference on the PEM at 12 months post-treatment is the threshold at which differences become relevant to the patient, and represents an appropriate non-inferiority margin. An effective sample size of 568 participants (284 per arm) is required to obtain 90% power to assess non-inferiority of collagenase based on the upper limit of a two sided 95% confidence interval (CI) (equivalent to a one-sided 97.5% CI) for the treatment difference ( $\delta = \text{collagenase} - \text{surgery}$ ) at 12 months post treatment, assuming a non-inferiority margin of 6 points and a standard deviation of 22 points. This calculation is based upon the sample size needed for 90% power in a one-sided independent samples t-test of size 2.5%, of  $H_0: \delta \geq 6$  vs  $H_1: \delta < 6$ , ignoring informative baseline covariates (reference joint and baseline PEM score). If  $\delta = 6$ , then we would expect the null hypothesis that collagenase is inferior to surgery to be rejected in 2.5% of hypothetical repetitions of the trial. If  $\delta = 0$ , then we would expect the null hypothesis that collagenase is inferior to surgery to be (correctly) rejected in 90% of hypothetical repetitions of the trial (assuming an analysis based on a one sided independent samples t-test of size 2.5%). Assuming 20% attrition at the 12 month follow up, the total target sample size is 710.

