### 8.3.1 Missing data

The model used for the primary analysis assumes that missing outcome data are missing at random (MAR) conditional on the fixed effects and non-missing outcomes included in the model. We will use multiple imputation to relax this MAR assumption by imputing missing values conditional on additional pre and post randomisation variables. We will also conduct analyses to investigate the sensitivity of the results to various systematic departures from MAR.

We will initially explore whether there are any obvious patterns of missingness in relation to outcome or baseline characteristics. Reasons for withdrawal and timing of withdrawal will be summarised to examine the extent to which withdrawal is driven by mechanisms plausibly related to outcome and/or treatment allocation. Unadjusted mean PEM score trajectories will be plotted for participants dropping out at each time point (both in aggregate and by allocation).

Associations between key baseline characteristics and missing outcome data and/or withdrawal prior to treatment will be explored using three sets of Firth logistic regression models [9]. Missing values of continuous baseline covariates will be mean imputed when fitting these models. The following baseline characteristics will be assessed

- Age (continuous)
- Sex (male or female)
- Smoking status (current, previous or never)
- Alcohol use (does drink alcohol or doesn't drink alcohol)
- Previous treatment with either limited fasciectomy or collagenase (previous treatment or no previous treatment)
- Presence of comorbidities (Yes or No)
- Number of digits affected (treated as continuous)
- MHQ score (continuous)
- URAM score (continuous)
- EQ-5D general health VAS score (continuous)

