Further treatment	Binary	No further treatment = 0, Further treatment = 1. Defined as additional treatment to the reference digit with collagenase, limited fasciectomy, dermofasciectomy or percutaneous needle fasciotomy	Logistic regression (with data augmentation if necessary)

The length of burn in will be determined by examining the trace plots of the chained equations algorithm, with a minimum burn in of 10 iterations being used if this appears to be sufficiently many for the algorithm to reach a stable state for all imputed variables. Imputed datasets will be analysed using the same model used for the primary analysis (without the Kenward-Roger degrees of freedom adjustment) with parameter estimates being combined according to Rubin's rules. The results will be reported in a similar manner to the reporting of the primary analysis results (Appendix E-2)

We will also investigate the sensitivity of results to departures from missing at random by imputing missing primary outcome data under a range of missing not at random scenarios. This will follow a pattern mixture modelling approach as implemented in the user contributed Stata command `rctmiss` [10]. At present this command does not support the covariance pattern model used for the primary analysis. We will therefore only use the outcome data from the 12 month post-treatment time point and use a substantive analysis based on analysis of covariance. Two versions of this analysis will be conducted; one including only patients who did not withdraw prior to treatment, and one including all randomised patients. The substantive analysis models will include allocation, study reference joint and baseline PEM score as predictors, with clustering by centre accounted for using a cluster robust standard error. Imputation will be performed allowing the sensitivity parameter of the pattern mixture model to vary from 0 (mean score among those with missing outcome data is the same as the mean score among those with non-missing outcome data, conditional on the covariates) to +/-10 (mean score among those with missing outcome data is +/-10 points larger/smaller than among those with non-missing outcome data, conditional on the covariates) in each group separately and across both groups. The tabular and graphical summaries used to report the results of these sensitivity analysis are given in Appendix E-2.

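### The missing-not-at-random analysis of 12-month PEM does not start from the primary model's missing-at-random assumption, so its delta is not measured from the assumption under test

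*SAP*

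**What the plan says.** SAP 8.2.3 models PEM at 3, 6, 12 and 24 months jointly with an unstructured covariance matrix. SAP 8.3.1 states what this model assumes about missing scores: they are "missing at random (MAR) conditional on the fixed effects and non-missing outcomes included in the model". A person seen at 6 months and then lost thus contributes the 6-month score to the 12-month comparison.

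SAP 8.3.1 then plans two further analyses that matter here.

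- **Multiple imputation at random.** "A total of 250 imputations will be generated using multiple imputation by chained equations". The imputation model (Table 3) contains all four post-treatment PEM scores, and each dataset is analysed with the primary model. No shift is applied to the imputed values. Outcomes are imputed only for patients who did not withdraw before treatment.
- **Departures from missing at random.** A pattern mixture analysis with the command rctmiss. Because this command does not support the covariance pattern model, the analysis will "only use the outcome data from the 12 month post-treatment time point". The predictors are allocation, reference joint and baseline PEM, with a cluster-robust standard error for centre. The sensitivity parameter delta runs from 0 to +/-10. Zero means that missing and observed 12-month scores have the same mean given those covariates. It is run once without patients who withdrew before treatment and once in all randomised patients.

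**The concern.** A delta analysis answers one question: how far from the primary assumption must one move before the conclusion changes? That requires delta = 0 to stand for the primary assumption. Here it does not. The primary model conditions on interim PEM and the delta analysis does not, so someone with a poor 6-month score who is then lost is treated like someone with the same joint and baseline PEM who was never seen after treatment.

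Appendix E-2 titles the results table as an exploration of departures from missing at random, so a reader will take its delta = 0 row as the assumption of the primary analysis. If that row is offset, part of the planned range of delta goes on making up for information that the observed 3- and 6-month scores already hold. Non-inferiority is judged on one confidence limit against 6 points, so even a modest shift can change how robust the result looks.

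The reason given is a software limit, yet the plan already generates imputed datasets that condition on the interim scores.

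**Working it through.** **The plan's own figures.** SAP section 3 gives the scale of the outcome: "assuming a non-inferiority margin of 6 points and a standard deviation of 22 points", with "90% power in a one-sided independent samples t-test of size 2.5"%. The normal approximation gives n per arm = 2 x (1.960 + 1.282)^2 x 22^2 / 6^2 = 282.5, so 283. The exact t-test power is 0.8995 at 283 and 0.9005 at 284 per arm, so the stated 284 per arm (568) is right. For the total, 568 / (1 - 0.20) = 710, as stated. The SD of 22, the margin of 6 and the 20% attrition can be used as they stand.

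**The two zero points.**

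| | Primary model | Delta analysis at 0 |
|---|---|---|
| Outcomes used | PEM at 3, 6, 12, 24 months | PEM at 12 months |
| Missing scores exchangeable given | allocation, joint, baseline, observed PEM at other visits | allocation, joint, baseline |
| Centre | random intercept | cluster-robust standard error |
| Participants | at least one post-treatment PEM | not withdrawn before treatment; all randomised |

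The second row shows that the assumptions differ, whatever the size of the effect.

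**How far delta reaches.** A shift of delta in one arm moves the treatment difference by about (fraction missing in that arm) x delta. At the plan's attrition this is 0.20 x 10 = 2.0 points at the end of the range.

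**How large the offset can be.** Large simulation, true difference 0. From the SAP: SD 22 and 20% missing at 12 months, taken as equal in the two arms. Assumptions not in the SAP: correlation 0.7 between 6- and 12-month PEM and 0.4 with baseline; everyone lost has a 6-month score; loss at 12 months is logistic in 6-month PEM, with the log-odds slopes per SD shown. Missingness is then at random given the interim score, as the primary model supposes.

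| Slope, collagenase | Slope, surgery | ANCOVA at delta = 0 | Also given 6-month PEM |
|---|---|---|---|
| 0.3 | 0 | -0.7 | about 0 |
| 0.5 | 0 | -1.2 | about 0 |
| 0.5 | 0.3 | -0.4 | about 0 |
| 0.5 | 0.5 | about 0 | about 0 |
| 0 | 0.3 | +0.7 | about 0 |
| 0 | 0.5 | about +1.1 to +1.2 | about 0 |

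The difference is collagenase minus surgery and higher PEM is worse, so a negative offset favours collagenase.

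As a share of the margin, 0.4 / 6 = 7% and 1.2 / 6 = 20%. For collagenase-only dropout the unrounded offsets are -0.73 and -1.16. The delta in the collagenase arm that would cancel them is 0.73 / 0.20 = 3.7 and 1.16 / 0.20 = 5.8.

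If only half of those lost have a 6-month score, the collagenase-only offsets fall to about -0.4 and -0.6.

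Steeper slopes give more. With 0.7 to 1 per SD and between-visit correlations of 0.5 to 0.8, offsets ranged from about 0 (same mechanism and rate in both arms) through -1.2 to -2.4 (slope 1 in collagenase only, 20% missing in each arm) to -4.9 (opposite mechanisms in the two arms). Those larger values need strong dropout dependence, and the most extreme needs opposite mechanisms. The 0.4 to 1.2 range is the more moderate guide.

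**The case against.** The strongest defence is that the described harm is handled elsewhere. Loss after a poor observed 6-month score is missing at random given observed outcomes, which both the primary model and the planned multiple imputation allow for. The plan also plots PEM trajectories by time of dropout and allocation. The non-inferiority decision rests primarily on the primary model. The compromise is disclosed, delta = 0 is defined, and Appendix E-2 reports the primary, imputed and delta = 0 estimates, so an offset would be visible. All of this stands, and it limits the weight of the point. It does not restore the zero point: no planned analysis applies a shift around an assumption that uses the interim scores.

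Four stronger readings are tempting and are not supported.

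- *That the ANCOVA's assumption is the stronger of the two.* Missing at random given baseline, and given baseline plus interim scores, are different conditions. Neither implies the other in general.
- *That the offset favours collagenase.* This needs dropout to depend on interim PEM more strongly in that arm. Nothing in the SAP says so; the reverse gives an offset of similar size against collagenase.
- *That observed scores are lost to the decision.* They are unused only in this sensitivity analysis.
- *That the table says nothing about robustness.* Delta moves the estimate by roughly missing fraction x delta, and a reader could apply that shift to the primary estimate by hand.

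It is also fair that replacing the rctmiss analysis outright would lose its all-randomised version, and that a delta conditional on the many variables of Table 3 is harder to interpret than one conditional on joint and baseline.

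**Conclusion.** The point holds as a mismatch of assumptions. The delta analysis in SAP 8.3.1 takes as its zero a condition that ignores observed 3-, 6- and 24-month PEM, so its delta is not the distance from the primary model's assumption. This follows from the text alone.

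The consequence is conditional. Its sign and size cannot be known from the SAP. Under the moderate assumptions above, offsets in the unequal-dropout cases are about 0.4 to 1.2 points in either direction; they roughly halve if half of those lost lack a 6-month score and vanish if dropout works alike in both arms. Against the roughly 2 points that delta = 10 in one arm can produce, that is large enough to blur a tipping point. It does not put the primary result in doubt. The change is a cheap improvement to a sensitivity analysis.

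**What to change.** Make delta-adjusted multiple imputation the main analysis of departures from missing at random. In the 250 imputed datasets of SAP 8.3.1, add delta to the imputed 12-month PEM values in the collagenase arm, the surgery arm or both, refit the primary model as already planned for imputed data, and pool by Rubin's rules. Delta = 0 then equals the planned imputed analysis. That is not identical to the primary model, because the imputation uses more variables and a slightly different set of patients, but it does condition on the interim PEM scores.

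Keep the rctmiss ANCOVA as a supplement in both versions. Its all-randomised version is needed because the imputed datasets do not impute outcomes for patients who withdrew before treatment. State beside its table that its delta = 0 conditions on allocation, joint and baseline PEM only.

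Cost: SAP wording and computing time, with no new data. The grid in Appendix E-2 has 20 non-zero deltas x 3 arm settings + 1 = 61 distinct settings, hence 61 x 250 = 15,250 model fits. Steps of 2 points would leave 10 x 3 + 1 = 31 settings, or 31 x 250 = 7,750 fits, and fewer imputations per delta would reduce this further.
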